# 8. Research plan

**Design:** This research study incorporates four stages:

- 1) Evidence synthesis: systematic review of behavioural techniques, theoretical underpinning of effective interventions in RCTs; systematic review of qualitative and observational research for potential 'active ingredients' of effective interventions for people with early frailty; policy review.
- **2) Qualitative study:** in-depth interviews with older people with early frailty and focus groups with carers, home care workers and community health professionals.
- **3) Development and manualisation of an intervention** using co-design methodology and a series of stakeholder panel meetings, hosted by Age UK London, KCL and UCL.
- **4)** Feasibility study with 50 people recruited from 4 General Practices in London and Hertfordshire individually randomised to the intervention and treatment as usual.

The intervention will be the first of its kind specifically developed for home-based health promotion for older

people with early frailty. We will engage with key organisations and representatives throughout the process, including older people with early frailty, carers, home care workers, community health professionals,

primary care health professionals, adult social care, public health, voluntary sector (Age UK) and public representative organisations (Healthwatch), commissioners/policy makers (Clinical Commissioning Groups CCGs, Local Health and Well-being boards LH&WBs) and experts in ageing and behaviour change. The research team itself is a strong multi-disciplinary team from a range of backgrounds including clinical (primary care and nursing), social care and social policy, health psychology, health economics and statistics supported by collaborators experts in health psychology/behaviour change, health economics, the voluntary sector, CCGs, LH&WBs and 3 experienced PPI representatives. We have substantial experience in research including systematic reviews, behaviour change, qualitative studies, health economics and trials of complex interventions. We have particular expertise in developing, delivering and evaluating complex interventions for older people in community settings.

# 9. Health technologies being assessed

This study's aim is to develop, manualise and feasibility test a new health technology. The intervention development will follow MRC guidance for the development of complex interventions. Components of the intervention will be clearly specified following the development stage including the evidence review and empirical qualitative study of 'active ingredients' of effective interventions, and the intervention delivery defined by the co-design process. It will be based on a theoretical framework, including an assets-based approach and the Baltes' model of selective optimisation and compensation (see description below). The theoretical framework underpinning past effective interventions determined by our evidence review will also be considered. Components are likely to include initial assets/risk profile; the older person identifying and selecting life goals to optimise; behavioural techniques to optimise these goals, promoting coping and the maintenance of function; development of compensatory mechanisms to address deficits. The behavioural techniques used will be those demonstrating the best evidence of effectiveness with this population in the evidence review, or if a lack of evidence for those with early frailty, then effective techniques with other similar populations. The intervention could include an assets based approach identifying what older people are able to do and wish to continue, with the older person setting goals, problem-solving to support optimisation of these goals and behaviour change, and signposting/facilitation of use of services to aid compensatory mechanisms, such as mobility aids, technology, or low vision services. For example, an asset might be identified that the older person can still get a taxi to visit their daughter/grandchildren, although this is becoming increasingly difficult with tiredness/weakness (a feature of frailty) and concerns about occasional urinary incontinence. In order to preserve this asset, the intervention might include advice and goal setting on physical activity/resistance training and diet to increase strength, a problem solving approach to support change/coping and signposting on provision of incontinence pads as a compensatory mechanism.

We will provide a translator for participants unable to speak/understand English and will be sensitive to older people's communication needs more generally. Intervention delivery will be specified in the co-design development process, but is anticipated to be of low-moderate intensity, with an initial assessment visit at home, followed by up to a maximum of 6 further home-visits or telephone contacts tailored to the individual. The 'person-specification' and related training requirements of the health professional delivering the intervention will be agreed in the co-design process, and will include training in the use behavioural techniques for health promotion in older people. The right skill-mix of the individual will be considered alongside cost to the NHS for intervention delivery. Currently in the NHS Health Trainers deliver behaviour change interventions at relatively low cost, and are widely available across England and may be a suitable option with specific training .

# 10. Theoretical/conceptual framework

A number of theories of successful ageing are important to consider in the development of a new

intervention for those with early frailty. Early important theories include activity theory and disengagement theory, where social engagement and activity is considered vital for successful ageing to occur. Whilst not the central underpinning theory for our approach, these theories have relevance in broadening the

scope of an intervention beyond a bio-medical model of disease prevention and reduction of disability. For older people the concept of resilience is also considered by many to be key, variously defined as the "dynamic process encompassing positive adaption within the context of significant adversity" 71. An application of resilience theory seen in Baltes' model of successful aging based on 'selective optimisation and compensation' is particularly relevant for an intervention for older people who are starting to become frail and face changes or adversity which require adaptation. Use of this model for our intervention would involve, for example, the selection of new or transformed goals in life by the older person, which are then optimised using changes in behaviours, and compensatory mechanisms are identified and promoted to tackle deficits. An intervention based on resilience theory might also focus on the development of resiliency traits, such as self-efficacy and draw on past experiences of loss and coping. A further key concept underlying our intervention is the use of an assets-based model that would focus on identifying and maintaining what people are still able to do to prevent a decline into increasing frailty. More widely used deficits models (identifying problems and needs to be addressed) tend to define individuals in negative terms, disregarding what is positive and works well. In contrast an 'assets' model would accentuate positive capability to identify problems and activate solutions. Assets models focus on promoting salutogenic resources that promote self esteem, self-efficacy, problem-solving and coping abilities, leading potentially to less dependency on professional services. This has particular relevance for those with early frailty, who are facing some problems, for example with fatigue and weakness, but still have a reserve of function and capabilities that it is important to identify and maintain.

# 11. Target population

Older people 65+ years with early frailty in receipt of community health services/visited at home by a health professional in the previous 6 months.

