# 4. Study synopsis

| Title                   | Home-Based Health Promotion for Older People with Early          |
|-------------------------|--|
|                         | Frailty  |
| Methodology             | Qualitative (interviews and focus groups) and quantitative (RCT) |
| Research Sites          | University College London (in collaboration with King's          |
|                         | College London, University of Hertfordshire, and St              |
|                         | George's University of London)                                   |
| Objectives/Aims         | To develop and test feasibility/acceptability and costs of a     |
| •                       | home-based health promotion intervention for older               |
|                         | people with early frailty  |
| Research Plan           | 1. Evidence synthesis: systematic reviews                        |
|                         | 2. Qualitative study: Interviews with older people with          |
|                         | early frailty and focus groups with carers, home care            |
|                         | workers, and community health professionals                      |
|                         | 3. Development and manualisation of an intervention: use         |
|                         | of co-design methodology and stakeholder panel meetings          |
|                         | 4. Feasibility study: Randomised Controlled Trial                |
| Number of Participants  | 10 older people with early frailty for interviews                |
|                         | 40 carers, home care workers, and community health               |
|                         | professionals for focus groups                                   |
|                         | 50 older people with early frailty for feasibility study         |
| Main Inclusion Criteria | Aged 65 or over; score as 'pre-frail'; community-dwelling;       |
|                         | life expectancy >6 months; capacity to consent to                |
|                         | participation  |
| Analysis                | For the qualitative study thematic analysis will be              |
|                         | undertaken.  |
|                         | For the feasibility study, analysis will be mainly descriptive   |
|                         | of the recruitment, participant characteristics, baseline        |

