from the reviews, theory and qualitative findings. The intervention will be delivered by health professionals at home for older people with early frailty, and will include use of theory-based behaviour change techniques.

**Feasibility study:** We will conduct a feasibility study with randomisation with older people in the target population registered with 4 General Practices in 2 different locations. General Practices will identify individuals receiving home visits and invite them to take part. Those eligible will be randomised to receive the intervention or treatment as usual. Intervention visits will be recorded and assessed for content/fidelity.

All people taking part will get a letter with a booklet listing local services/contacts that may be useful to them. Participants will be followed up for six months.

**Outcomes:** A theory-based intervention tested for acceptability/feasibility in community settings. Data on patient recruitment/willingness to be randomised, attrition, acceptability of assessments and potential outcomes for an RCT: quality of life (EQ-5D); functioning (modified Barthel, ); frailty (Frailty Index); mobility (gait speed); grip strength; well-being (S-WEMWBS); psychological distress (GHQ-12); uptake preventative interventions; CVD risk factors (Body Mass Index (BMI), physical activity-IPAQ, smoking, alcohol-AUDIT-C), falls; medication use; Cognition (MoCA) service utilisation (NHS/social care, CSRI); costs (health and social care, out of pocket expenses, cost to carer); quality adjusted life years (QALYs); Capability Adjusted Life Years (ICECAP-O); mortality.

**Sample size:** To test feasibility we will identify 12-13 eligible older people per GP practice, in 2 practices per locality (target: 50 participants). This was feasible in our previous work.

**Management:** The project will be led by UCL, with monthly meetings with the core team (co-investigators), overseen by a multi-disciplinary advisory group meeting 6 monthly. Key project milestones: Month

- 0-6: Evidence searching/extraction/coding; focus groups, in-depth interviews.
- 6-12: Evidence synthesis, qualitative analysis, develop/manualise intervention with panels, ethics/governance amendments
- 12-18: Site initiation for feasibility study, training intervention delivery.

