### **Inclusion/Exclusion Criteria**

*Inclusion criteria:* Registered with one of participating General Practices; aged 65 or more; score as 'mild frailty' on the Clinical Frailty Scale; community-dwelling (including people living in extra care housing); life expectancy > 6months; capacity to consent to participate in this research (including those with dementia or communication difficulties who retain capacity to consent). We will include participants who are not able to communicate in English, if they can provide informed consent, assisted if needed by a translator.

**Exclusion criteria:** Those living in care homes (likely to have established frailty); on GP palliative care register; those who lack capacity to consent (e.g. advanced dementia); those already case managed (e.g. by community matrons, some reablement schemes).

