# Feasibility study:

Sampling strategy: We will select 2 practices each in our 2 study areas (London Borough of Camden and Hertfordshire) to ensure a diverse representation of older people living in urban, suburban, and rural communities and from diverse socio-economic and ethnic backgrounds. The London Borough of Camden has a very socially and ethnically diverse population, while there are higher proportions of older people (and very old people) in Hertfordshire with differences in access to health, transport and other services. Participants will be identified through database searches of GP lists of registered patients over 65, excluding those with recorded exclusion criteria (e.g. those on the GP palliative care register). These lists will be further screened by participating GPs for eligibility criteria and exclusions removed. Remaining participants will be approached by letter by their GP with a study information leaflet. A telephone reminder will be made to non-responders by a member of the practice team. Those expressing an interest will be contacted by the research nurse for initial telephone eligibility screening. GPs will also be able to refer people opportunistically to the study, e.g. those they are visiting/have visited at home recently who did not meet criteria for existing frailty services. Potentially eligible participants (from telephone screening or GP referral) will then be visited at home to discuss participation, gain informed consent, full baseline assessment, and subsequent web-based randomisation.

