Sample size, recruitment and retention: For the feasibility study we aim to recruit 50 people, 12-13 each from 4 General Practices. This number was selected as a sufficient number to test the feasibility/ acceptability of the intervention and pilot the study process, recruitment, randomisation and retention for a full RCT, and a realistic number to recruit per practice and deliver the intervention in the short time frame available for the feasibility study. Assuming an average of 600 people aged over 65 per study practice (based on our previous studies with this age group in our study settings), a prevalence of 41% of 'pre-frailty'38 would lead to a population of 246 before exclusions. Assuming (on best estimates) 30 of these are excluded, and 20% have been visited at home in the last 6 months by a health professional (including GPs, Out of Hours services, nurses, health care assistants, physiotherapist, occupational therapist or other community health professional) our eligible population would be 43 people. Assuming a conservative recruitment rate of 30% of eligible people, we could recruit 13 people per practice. In our past experience in previous studies on health promotion in the 65+ population (the WISH study) our attrition (including deaths) over 3 months was 10% and over 6 months 23%. Part of the purpose of the feasibility study is to assess if all of these assumptions are correct, as there is no data available (apart from community prevalence) that are specific to an older population with early frailty with which to base these assumptions. If our eligibility or recruitment rate is much lower than anticipated we would be able to extend our study to include further GP practices.

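### The home-visit restriction that defines the target population and drives the recruitment forecast is absent from the inclusion criteria and the GP search, so the eligible pool is about 216 or about 43 per practice depending on which section is followed

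*Protocol*

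**What the plan says.** **Where the restriction appears.**
- Protocol Section 11 (Target population) describes people aged 65 and over with early frailty who are "in receipt of community health services/visited at home by a health professional in the previous 6 months".
- Section 5 (Feasibility study) says that "General Practices will identify individuals receiving home visits and invite them to take part", without a time window.
- Section 13 (Sample size, recruitment and retention) multiplies by the 20% assumed to have had a home visit in the last 6 months and concludes that "our eligible population would be 43 people" per practice.

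**Where it does not appear.**
- The inclusion and exclusion criteria in Section 11, directly below the target population, cover practice registration, age, frailty, community dwelling, life expectancy and capacity. They contain no item on home visits or community services.
- The synopsis (Section 4) lists "Aged 65 or over; score as 'pre-frail'; community-dwelling", then life expectancy and capacity, and no such item.
- The recruitment procedure in Section 13 says: "Participants will be identified through database searches of GP lists of registered patients over 65, excluding those with recorded exclusion criteria". GPs then screen the list against the eligibility criteria, and everyone remaining is written to. A recent home visit is mentioned there only as an example of whom a GP might refer opportunistically.

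**Frailty category.** Section 11 requires people who "score as 'mild frailty' on the Clinical Frailty Scale". The synopsis asks for pre-frail and names no instrument. Section 5 treats mild and pre-frail as alternatives. The Section 13 forecast uses a pre-frailty prevalence.

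**The concern.** A practice that follows the listed criteria and the Section 13 search could invite and enrol people outside the Section 11 target population without departing from any listed criterion. The forecast, meanwhile, counts only people inside it.

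In this study the rates are a main product. Section 13 says that part of the purpose is to find out whether the eligibility and recruitment assumptions are correct. Section 14 collects eligibility and uptake for a CONSORT diagram, and objective 4 in Section 7 is to test recruitment for a full trial. If the step that produces the 20% factor is not applied in the field, that factor is not observed, and an observed uptake cannot be set against the assumed 30%. Eligibility and the identification of participants belong in the protocol, so a separate analysis plan would not settle this.

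**Working it through.** **Inputs, all from Protocol Section 13 (Sample size, recruitment and retention):**
- List size: "Assuming an average of 600 people aged over 65 per study practice".
- Prevalence of pre-frailty: 41%.
- Exclusions: 30 per practice.
- Share visited at home in the last 6 months: 20%.
- Recruitment rate among eligible people: 30%.
- Target: 50 people from 4 practices, 12-13 each.

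**Step 1: reproduce the plan's forecast.**
- Pre-frail: 600 × 0.41 = 246. The plan agrees ("would lead to a population of 246 before exclusions").
- After exclusions: 246 − 30 = 216.
- After the home-visit factor: 216 × 0.20 = 43.2, stated as 43.
- Recruits: 43.2 × 0.30 = 12.96, stated as 13.
- Four practices: 4 × 12.96 = 51.8, against a target of 50.

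The forecast is arithmetically correct.

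**Step 2: apply the criteria and search as written.** Without the home-visit factor the eligible pool is 216 per practice, or 4 × 216 = 864 in total, against 4 × 43.2 = 173 with it. The ratio is 216 / 43.2 = 5.0.

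**Step 3: the same recruits on each denominator.**

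| Denominator per practice | Uptake if 13 are recruited | Recruits at 30% uptake |
|---|---|---|
| 43.2 (restriction applied) | 13 / 43.2 = 30.1% | 12.96 |
| 216 (criteria as listed) | 13 / 216 = 6.0% | 216 × 0.30 = 64.8 |

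For the full target, 50 / 173 = 28.9% and 50 / 864 = 5.8%.

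**Step 4: sensitivity.**
- Prevalence. Section 6 gives 44% from the same cited reference. Then 600 × 0.44 − 30 = 234, and 234 × 0.20 = 46.8. The ratio is still 5.0.
- Share meeting the restriction. If a share s of the 216 meets it, the ratio is 1/s. The figure of five comes wholly from s = 0.20. Section 11 also admits people receiving community health services, which may be a wider group than those visited at home. If s exceeds 0.20, the ratio is below five.
- Frailty wording. The protocol gives no prevalence for mild frailty on the Clinical Frailty Scale, so the effect of this mismatch cannot be calculated.

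**The case against.** **The target population statement can be read as the frame for the criteria.** It opens the section that holds them. That is a fair reading of the authors' intent, but the operative list and the search do not repeat the restriction, and those are what practices and the research nurse would apply.

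**The 6% and 30% figures are a conditional contrast.** They hold recruits at 13. At 30% uptake the wider pool would give about 65 per practice, and Section 13 allows further practices if recruitment is slow. This stands. The contrast shows that the denominator is ambiguous. It does not predict recruitment.

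**A reader might infer that a full trial would misjudge the number of practices five-fold.** The document does not support that. Practices needed equal the target sample divided by recruits per practice, and that yield is observed whichever denominator is used. A five-fold error would require a rate from one denominator to be applied to the other pool, and no step in the plan does so.

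**A reader might infer that progression depends on the denominator.** It does not: success criterion 1 in Section 16 is a count, 70% of 50 within 6 months. Equally, meeting that count would not reveal which population had been recruited.

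**A reader might infer that Section 5 imposes the 6-month limit.** It does not. Its target population has no home-visit rule, and its sentence on recruitment has no time window. The window stands only in the Section 11 target population and the Section 13 forecast. The remark in Section 23 that the population has difficulty leaving home supports a costing and is not an eligibility statement.

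**The frailty terms may mean one group to the authors.** Section 5 pairs mild with pre-frail, and Section 24 equates early frailty with pre-frail. This softens the point, but the criteria in Sections 4 and 11 still differ in wording, and only one names an instrument.

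**Conclusion.** The contradiction is real and should be resolved before recruitment. The restriction in the Section 11 target population, used numerically in the Section 13 forecast and reflected in Section 5, is not carried into the inclusion criteria or the search and GP screen. On the plan's own inputs the eligible pool is about 216 per practice under the criteria as listed and 43 under the forecast. The five-fold ratio rests on the 20% figure and would be smaller if the wider Section 11 wording covers more than 20%.

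The consequences are that the recruited population may differ from the target population, and that the observed eligibility and uptake could not be compared with the assumed 20% and 30%. The documents do not show an error in the number of practices for a full trial, or in the count-based recruitment criterion. The difference in frailty wording is a secondary point without a computable size. The document does not settle which population is intended.

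**What to change.** Choose one definition and use it throughout.

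- **If the restriction is intended:** add the Section 11 wording to the inclusion criteria in Sections 4 and 11, and to the Section 13 database search or the GP and telephone screens. Word the forecast to match Section 11, stating whether the 20% covers receipt of community health services as well as home visits.
- **If the wider population is intended:** remove the restriction from Section 5, the Section 11 target population and the Section 13 forecast. Restate the eligible pool as about 216 per practice, and the uptake needed for 12-13 recruits as about 6% (12 / 216 = 5.6%; 13 / 216 = 6.0%).

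Secondarily, use one frailty category and instrument in Sections 4, 5, 11 and 13. If no prevalence is available for the enrolled category, say that the 41% for pre-frailty is a proxy.

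The cost is protocol wording and, on the first route, one screening item. The downside of that route is that GP records may not capture every type of visit counted in the forecast, which includes out-of-hours services and community therapists. Part of the check may then fall to the telephone screen.
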